## **6.1 Study Monitoring Plan**

This study shall be monitored according to a monitoring plan. The PI shall allocate adequate time for such monitoring activities. The PI shall also ensure that the monitor or other compliance or quality assurance reviewer is given access to all the above noted study-related documents and study related facilities (e.g. pharmacy, diagnostic laboratory, etc.), and has adequate space to conduct the monitoring visit. The address is listed below. The monitoring procedures are a part of the sponsor's or its representative SOPs.

The monitoring shall be provided by a Canadian and Danish Clinical Research Organizations. Clinical Research Associates (CRA) will travel regularly to each site to perform the quality control of the data reported in the CRF.

## **6.2 Auditing and Inspecting**

The trial may be subject to review by the EC/CA and/or to quality assurance audits performed by the sponsor or its representative and/or to inspection by appropriate regulatory authorities.

It is important that the PI(s) and their medical staff are available during the monitoring visits and possible audits or inspections and that sufficient time is devoted to the process.

## 7. DEVICE LABELING

See Appendix 10.

The Neuro Zti system is CE marked, Health Canada registered and distributed/sold into the market of participating countries.

The device shall be ordered by the hospital and billed to the social security organization and/or insurance company and/or relevant purchasing authority.

## 8. CONSENT MATERIALS

See Appendix 2.

All parties shall ensure protection of all subjects' personal data and shall not include subject names on any sponsors forms, reports, publications or any other disclosures. In case of data transfer, Oticon Medical shall maintain a high standard of confidentiality and personal data protection.

The informed consent form must be agreed to by Oticon Medical and the EC and must be in compliance with ICH-GCP, ISO 14155 standard, local regulatory requirements and legal requirements.

The investigator must ensure that each subject is fully informed about the nature and objectives of the trial and possible risks associated with participation. The investigator shall obtain written informed consent from each subject before any trial specific activity is performed. The informed consent form used in this trial, and any change made during the course of the trial, must be prospectively approved by both EC and Oticon Medical before use. The investigator shall retain the original of each subject's signed consent form.

## **9. Ethical Committee (EC)/Competent Authority (CA)**

It is the responsibility of the investigator to have prospective approval of the trial protocol, protocol amendments, informed consent forms and other relevant documents from the EC/CA. All correspondence with the EC/CA shall be retained in the investigator file. Copies of the EC/CA approvals shall be forwarded by Oticon Medical or its representative.

The only circumstance in which an amendment may be initiated prior to EC/CA approval is where the change is necessary to eliminate an apparent immediate hazard(s) to the subjects. In such cases, the investigator shall notify the EC/CA and Oticon Medical or its representative within 5 working days after the implementation.

The trial shall be performed in accordance with the protocol, International Conference on Harmonization of Good Clinical Practice guidelines, the declaration of Helsinki (Appendix 11), ISO 14155:2011 standard and all applicable local regulatory requirements and laws.

## 10.ADDITIONAL RECORDS AND REPORTS

### 10.1 Data Handling and Record-Keeping

#### 10.1.1 Case Report Form

As used in this protocol, the electronic Case Report Form (eCRF) should be understood to refer to an electronic data record depending on the data collection method used in this trial.

A CRF is required and should be completed for each subject. The completed original CRFs are the sole property of the sponsor. The CRFs shall not be made available in any form to third parties without written permission from the sponsor. Written permission is not required if the data is requested by the authorized representative(s) of the sponsor or an appropriate regulatory/legal authority.

It is the investigator's responsibility to ensure completion and to review and approve all CRFs. CRFs must be signed by the investigator or by an authorized staff member. These signatures serve to attest that information contained on the CRFs is true and correct. At all times, the investigator has final personal responsibility for the accuracy and authenticity of all clinical and test/exams data entered on the CRFs. Subject source documents are the physician's subject records maintained at the trial site. In most cases, the source documents are the hospital or the physician's chart. Where the source documents are the hospital or the physician's chart, the information collected on the CRFs must match those charts.

The eCRF cannot be considered as source document for this trial. Accurate and reliable data collection is ensured by the study monitor (source document verification).

The Electronic Data Capture system is compliant with the 21CFR part 11 FDA.

#### 10.1.2 Subject Confidentiality

Information about the patients shall be kept confidential and managed according to the requirements of the Personal Data Protection law. Those regulations require a signed subject's authorization informing the subject of the following:

- What protected health information (PHI) will be collected from subjects in this study
- Who will have access to the information and why
- Who will use or disclosure that information
- The rights of the subject to revoke their authorization for use of their personal health information

*Note: This information and the subject's authorization shall be provided to the subject in the informed consent form.*

In the event that the subject revokes authorization to collect or use their information/data, the PI, by regulation, retains the ability to use all information collected prior to the revocation of subject authorization. For subjects that have revoked authorization to collect or use PHI, attempts should be made to obtain permission to collect at least safety status at the end of their scheduled study period.

To maintain subject confidentiality, the site number, the subject inclusion number and subject initials (SSID) will identify all study subjects on CRFs and all other documentation submitted to the Sponsor.

#### **10.1.3 Source Documents**

*Source Data* are the clinical findings and observations, laboratory and test data, and other information contained in the Source Documents.

*Source Documents* are the original records (and certified copies of original records); including, but not limited to, hospital medical records, physician or office charts, physician or nursing notes, subject diaries or evaluation checklists, pharmacy dispensing records, recorded data from automated instruments, x-rays, CT Scans, MRI, etc. When applicable, information recorded on the CRF shall match the *Source Data* recorded in the *Source Documents*.

Study data shall be recorded directly on the CRF, whereupon the CRF data is to be considered the *Source Data*. Descriptions of these specific data shall be attributable, legible, original and accurate and must meet the regulatory requirements for recordkeeping. Source documents include all documents, images, files, and folders containing subject's medical data.

### **10.2 Record Maintenance and Retention**

To enable evaluations/audits from regulatory authorities or Oticon Medical, the PI agrees to keep records, including the identity of all participants (e.g. Hospital records, CRFs, sufficient information to link records), all original signed informed consent forms, copies of all CRFs, serious adverse event forms, source documents and detailed records of device fitting/disposition. The records shall be retained by the PI according to ICH, local regulation, or as specified in the Clinical Study Agreement, whichever is longer.

If the investigator relocates, retires or for any reason withdraws from the study, the sponsor shall be prospectively notified. The study records must be transferred to an acceptable designee such as another investigator, another institution, or to the sponsor. The investigator must obtain the sponsor's written permission before disposing of any records, even if retention requirements have been met.

A unique subject identification code is assigned to each subject to protect subject identity. This unique code is used to identify the CRF, adverse events reports or other study-related data. These unique subject identification codes shall be recorded on the subject identification code list and kept in a confidential manner in the investigator site file. To protect subject identity, the subject names or other directly identifiable information shall not appear on any reports, publications, or other disclosures of clinical study outcomes.

### **10.3 Data Management Procedures**

The data will be entered into a validated database. The sponsor or its representative shall be responsible for data processing, in accordance with procedural documentation. Database lock shall occur once quality assurance procedures have been completed.

All procedures for the handling and analysis of data shall be conducted using good computing practices meeting FDA guidelines for the handling and analysis of data for clinical trials.

## **10.4 Data Quality Control and Reporting**

After data have been entered into the study database, a system of computerized data validation checks shall be implemented and applied to the database on a regular basis. Query reports (Data Clarification Requests) pertaining to data omissions and discrepancies shall be forwarded to the PIs and study monitors for resolution. The study database shall be updated in accordance with the resolved queries. All changes to the study database shall be documented.

## **10.5 Archival of Data**

Appropriate backup copies of the database and related software files shall be maintained. Databases are backed up by the database administrator in conjunction with any updates or changes to the database. At critical junctures of the protocol (e.g., production of interim reports and final reports), data for analysis is locked and cleaned per established procedures.

## **10.6 Clinical Trial Registration**

This trial shall be registered in [www.clinicaltrials.gov](http://www.clinicaltrials.gov), and results reported as required.

## **10.7 Publication**

Neither the complete nor any part of the results of the study carried out under this protocol, nor any of the information provided by the sponsor for the purposes of performing the study, shall be published or passed on to any third party without the written consent of the study sponsor. Any PI involved with this study is obligated to provide the sponsor with complete test results and all data derived from the study.

### 1.1 General description of device, intended uses, and model designations

The Neuro Zti cochlear implant system is a cochlear implant system consisting of the Neuro Zti implant, Neuro One sound processor and all components and accessories for the final user, and DigiMap software interface, and surgical tools for clinic.

The present technical file describes the “Neuro Cochlear Implant System”. The Neuro Cochlear Implant System is the fourth generation developed by Neurelec and the first cochlear implant to be developed and marketed by Oticon Medical. The intended use of the investigational device is to provide access to sound via direct electrical stimulation of the auditory nerve for adults and children suffering from severe to profound hearing loss. The Neuro Cochlear Implant system’s components (external and surgically implantable), electrical stimulation parameters and mechanism of action are essentially the same as approved predicate cochlear implant devices. The implanted component is the Neuro Zti receiver/stimulator with associated electrode arrays and the external component is the Neuro One sound processor. The implantable receiver/stimulator (Neuro Zti) may be configured with one of two different electrode arrays. The array model designations are the “Classic” array and the “EVO” array; the product configurations are labeled as Neuro ZtiCLA and Neuro ZtiEVO, respectively.

The device description herein has been modeled after guidance provided in the AAMI-CDV-4 CI86 guideline

The system including fitting interface, processor and implantable component are shown in figure 1 below:

[figure not shown]
**Figure 1:** Schematic of the Neuro cochlear implant system including fitting components.

## 1.2 Specific inventory of system components and their essential functions

### 1.2.1 Implantable components

#### 1.2.1.1 Receiver-stimulators

The system has a single receiver/stimulator model, The Neuro Zti. The Neuro Zti is designed to be surgically placed under the periosteum on the temporal aspect of the skull. Unlike predicate cochlear implant receiver/stimulators approved by the FDA, the Neuro Zti features an integrated fixation system which allows fixation to the skull using two self-tapping titanium screws. A schematic of the dimensions of the Neuro Zti can be seen in Figure 2. The Neuro Zti Cochlear Implant consists of electrical components hermetically encased within a mechanical housing made from zirconia and titanium. This housing is connected to a 20 contact multi-channel electrode-array with an integrated reference electrode located on the lead close to the receiver/stimulator. The feedthroughs in the housing enable the connection between the internal electronics and the electrode array. A unique design feature of the receiver/stimulator is that it has an opening in the center designed to securely hold a removable/replaceable magnet. The purpose of this feature is to allow magnet removal for increased MRI compatibility. In addition to being able to provide electrical stimulation to the cochlea, the Neuro Zti is equipped with circuitry to enable use of the electrode contacts for the recording of electrically evoked compound action potentials (eCAPs).

[figure not shown]

**Figure 2:** Schematic of the Neuro Zti configured with the “Classic” array (Neuro ZtiCLA). Dimensions are in millimeters unless otherwise noted.

### 1.2.1.2 *Electrodes*

The Neuro Zti may be configured with either the “Classic” or “EVO” array; these two product configurations are designated as Neuro ZtiCLA and Neuro ZtiEVO, respectively. A schematic of the two electrode options can be seen in Figure 3, while detailed information regarding the arrays is further outlined in Section 1.5. The arrays are both constructed from the same raw materials with the contacts being machined from platinum/Iridium (10%). The wires between contacts and the receiver/stimulator are coated with PTFE for electrical isolation. The PTFE coated wires are completely embedded inside an over-molding comprised of medical grade silicone; therefore, the wires are not in contact with the tissues.

The principal differences between the two electrode array options are that the Neuro ZtiEVO has a slightly smaller form factor allowing for reduced stiffness and may be more suitable for “softer” surgery. Both arrays are currently approved for use in Canada and the European Union and have been used with the prior generation device, Digisonic SP. The company makes no specific warranty or prescription as to which array is most appropriate for a given patient; thus leaving the array choice to the preference of the surgeon. Furthermore, there are no specific restrictions as to the surgical approach to the cochlea (ie. traditional mastoidectomy vs transtympanic approach) or to the introduction of the array into the cochlea (round window vs cochleostomy approach). Both arrays may be inserted (and re-inserted if necessary) into the scala-tympani using the same techniques.

**Figure 3:** Schematic showing the EVO and CLASSIC electrode array options for the Neuro Zti

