#### **3.5.2 Electrode arrays**

The surgeon may elect to use one of two types of lateral-wall electrode arrays that are available for the Neuro Zti. The two electrode arrays are the Neuro ZtiCLA and the Neuro ZtiEVO. Both arrays have been extensively used OUS for several years on the prior generation implant and now in OUS implantations of the Neuro Zti. Both arrays provide 20 contacts, similar cochlear coverage and are amenable to round-window, modified round-window or cochleostomy insertions into the scala-tympani. To date, there is no evidence that speech perception outcome is impacted by the array choice and both of the array's dimensions are much smaller than the scala-tympani dimensions reported in the literature. Both arrays demonstrate stiffness profiles that fall within those demonstrated in existing designs by other manufacturers currently approved by the FDA. At present, the choice is left to the surgeon's preference. The principle difference between the arrays are that the "Classic" Array is slightly stiffer than the "EVO" making it slightly easier to achieve a full insertion. However, the less stiff EVO, is suspected to allow for a "softer" insertion which under certain conditions may result in a lower probability of cochlear trauma. To date, the EVO version is the most common electrode array used and the classic version tends to be used in cases of more difficult insertion due to anatomical issues or other issues that result in difficult insertion such as compromised patency of the scala-tympani due to fibrosis or ossification. Temporal bones studies have been conducted for both arrays and this data will also be provided in the PMA application.

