### **3.5.3.1 Allocation to Treatment**

Not applicable.

Open label-trial.

A single identification number (SSID) is assigned at the inclusion visit that uniquely identifies each subject, it is composed of the site code and subject number |\_|\_|-|\_|\_|. The same CI system models shall be assigned for all subjects. The sound processor is available in different colors but the hardware and electronic features are identical between processors.

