**TABLE 3: Specifications and characteristics of the Neuro ZtiCLA**

Identification number	M80184
Material components	Connecting wire: Platinum iridium 10% Stimulation electrode: Platinum iridium 10%
Number of independent active electrodes	20
Insertion length	26 mm
Active length	25 mm
Dimensions	Active area: 0.39 mm  to 0.77 mm  Diameter at apex: 0.5 mm Diameter at base: 1.07 mm
Reduced cochleostomy size	Diameter of 1 mm (may be inserted via round window)
General shape	Straight Straight: distance between electrodes and silicone, inferior to 0.1 mm
Shape at apex	Rounded shape
Shape at the base	Diameter push rings: 2x1.5 mm
Insulation	PE (polyester): wire Si (silicone): external tubing

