**TABLE 4: Specifications and characteristics of the Neuro ZtiEVO**

Identification number	M80185
Material components	Connecting wire: Platinum iridium 10% Stimulation electrode: Platinum iridium 10%

Number of independent active electrodes	20
Insertion length	25 mm
Active length	24 mm
Dimensions	Active area: 0.46 mm  to 0.60 mm  Diameter at apex: 0.4 mm Diameter at base: 0.5 mm
Reduced cochleostomy size	Diameter of 0.8 mm (may be inserted via the round window)
General shape	Straight Straight: distance between electrodes and silicone, inferior to 0.1 mm
Shape at apex	Rounded shape
Shape at the base	Diameter push rings: 1x1.5 mm & 1x1.2 mm
Insulation	PE (polyester): wire Si (silicone): external tubing

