## 5.5. Surgery

(refer to table 7)

- Ear implanted: Right / Left
- Cochlear implant type: Neuro Zti CLA / Neuro Zti EVO
- Full electrode array insertion : yes/no
- Number of electrodes out of cochlea,
- Time of surgery (min)

- Objective measures: Yes / No
  - If YES, performance of impedance and ECAP testings: Done / Not done / Meet an issue
  - If Impedance DONE: value (kilo ohms) for the 20 channels
  - If ECAP DONE: Download the results into the eCRF

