### **6.3.5. Measures of impedance in FAS and PPS**

The time course of electrodes impedance performed at each time points will be analyzed through a mixed model for repeated measures and contrasts of interest. (refer to table 15).

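### Impedance per electrode is averaged over two arrays with different contact areas, so each mean in SAP Table 15 and the channel comparison depend on the array mix

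*Protocol*

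**What the plan says.** Protocol 3.5.2 states: "The surgeon may elect to use one of two types of lateral-wall electrode arrays that are available for the Neuro Zti". Appendix 1, section 1.2.1.2 repeats that the choice is the surgeon's, "thus leaving the array choice to the preference of the surgeon". Section 3.5.2 adds that "the classic version tends to be used in cases of more difficult insertion due to anatomical issues", and that the EVO has been the more common array so far. Protocol 3.5.3.1, by contrast, says "The same CI system models shall be assigned for all subjects" and mentions only processor colour as varying.

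Appendix 1 specifies the arrays separately. Table 3 (CLA) begins its dimensions with "Active area: 0.39 mm"², rising to 0.77 mm². Table 4 (EVO) begins with "Active area: 0.46 mm"², rising to 0.60 mm². Active length is 25 mm and 24 mm. Table 5 gives a maximum charge density below 59 µC/cm² for the CLA and below 50 µC/cm² for the EVO.

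SAP 5.5 collects the array type ("Cochlear implant type: Neuro Zti CLA / Neuro Zti EVO"), and Table 7 counts it by language. SAP 5.8 then averages each electrode's impedance at each time point, and SAP 6.3.5 says the time course will be "analyzed through a mixed model for repeated measures and contrasts of interest". Protocol 3.6.2.4(e) left those contrasts to the SAP, which does not list them. Table 15 has one column per electrode, e1 to e20, with no split by array, and its model shell names only channel and visit. The shells in Tables 10, 12 and 14 do name patient.

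**The concern.** An average by electrode number can be interpreted if the number denotes the same kind of contact in every patient. Here the number identifies a position on one of two arrays whose contacts span different ranges of area. If impedance depends on contact area, the mean for a given electrode is a weighted average of two different quantities. Its weight is the share of CLA among the patients measured, which the plan neither fixes nor reports next to the impedance results.

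What is at stake is the technical-functionality description. A pooled mean could differ from one electrode to the next, or from a later series, because of contact geometry and array mix and not because of the state of the electrode-tissue interface. The pooled channel profile could also describe neither array.

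**Working it through.** **Plan's own figure.** The documents state no expected impedance by electrode or array, so there is nothing to reproduce. The inputs are the contact areas in Appendix 1, Tables 3 and 4, and the charge figures in Table 5.

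**Do the documents treat the contacts as electrically different?** Table 5 gives a maximum charge of 200 nC. Charge density is charge divided by area, and 1 nC/mm² = 0.1 µC/cm².
- CLA, smallest contact: 200 / 0.39 × 0.1 = 51.3 µC/cm²
- EVO, smallest contact: 200 / 0.46 × 0.1 = 43.5 µC/cm²

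Each lies under its own limit (59 and 50). The CLA value would exceed the EVO limit, so one common figure would not serve both arrays.

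**Spread of area within each array.** CLA: 0.77 / 0.39 = 1.97-fold. EVO: 0.60 / 0.46 = 1.30-fold. A single constant shift between arrays over all 20 channels is therefore unlikely.

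**Illustrative difference on one channel.** Assume (a) impedance is inversely proportional to area and (b) the smallest contacts of the two arrays share an electrode number, as do the largest. Neither is stated in the documents. Then EVO impedance / CLA impedance = CLA area / EVO area.
- Smallest contacts: 0.39 / 0.46 = 0.85, so EVO is 15% lower
- Largest contacts: 0.77 / 0.60 = 1.28, so EVO is 28% higher

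If assumption (b) is dropped and any extreme may pair with any other, the CLA/EVO impedance ratio under 1/area runs from 0.46 / 0.77 = 0.60 to 0.60 / 0.39 = 1.54. Under the weaker 1/√area, the same pairings give 0.77 to 1.24.

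**Effect on the pooled mean.** With EVO share w and EVO/CLA ratio r on a channel, pooled mean = CLA mean × [1 + w(r − 1)]. The split is not given; take w from 50% to 90% as an assumed range.
- r = 0.85: the pooled mean is 7.6% (w = 50%) to 13.7% (w = 90%) below the CLA mean
- r = 1.28: it is 14.2% to 25.5% above the CLA mean

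**Effect on the channel comparison.** Under (a) and (b), the impedance ratio of the smallest to the largest contact is 1.97 in the CLA and 1.30 in the EVO. The pooled ratio is [(1 − w)/0.39 + w/0.46] / [(1 − w)/0.77 + w/0.60].
- w = 50%: 2.369 / 1.483 = 1.60
- w = 90%: 2.213 / 1.630 = 1.36

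The same two devices give a different channel profile depending only on the mix.

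**Effect on the visit test.** A patient keeps the same array at every visit unless re-implanted. Visit differences are formed within patients, so a patient random effect removes a constant array shift from that comparison. It does not remove array-by-channel differences. The pooled means drift across visits only if the array mix among the patients measured changes.

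**The case against.** The strongest reply is that impedance here is a functionality check. Out-of-range electrodes are deactivated and counted, and Table 5 of Appendix 1 gives one normal range, 500 Ω to 7 kΩ, for the implant whichever array is fitted. Against a 14-fold range, a shift of 15% to 28% is small. That stands for the out-of-range counts. It does not rescue the per-electrode means or the channel term, which Table 15 reports as results in their own right. It is also fair that the EVO area range lies inside the CLA range and that the size rests on assumptions.

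A reader might infer more than the documents support:
- **That the protocol contradicts itself on which device is implanted.** Section 3.5.3.1 speaks of system models. Appendix 1 has a single receiver/stimulator model and calls CLA and EVO product configurations of it, and section 3.5.2 openly offers both. Yet Appendix 1 also uses the word model for the arrays, and the explantation form lists them as device models. The wording needs reconciling, but as an editorial matter.
- **That neither array's results can be seen.** Implant type is recorded per patient, and the explantation form records CLA or EVO. Results by array can be recovered; they are just not planned.
- **That array differences undermine the visit test.** With a patient effect fitted, they largely do not. The Table 15 shell omits patient, but SAP 6.3.5 calls for a repeated-measures mixed model, so the shell need not be the full model.
- **That the co-primary results are compromised.** The investigational device is the system. Section 3.5.2 gives a reason for pooling speech outcomes, though it says nothing comparable on impedance. The planned HINT-Q test and the complication rate remain what they claim to be for the system as used.

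**Conclusion.** The point holds for impedance and is minor. Each per-electrode mean in Table 15, and the comparison between channels, combines two contact geometries in proportions the plan does not control. The figure of about -15% to +28% for EVO relative to CLA is an illustration: it assumes impedance inversely proportional to area and matching extreme contacts. With the pairing left open, the data in Appendix 1 allow a CLA/EVO ratio anywhere from 0.60 to 1.54. The actual size cannot be determined without the area by electrode number and the array split.

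No conclusion on the primary HINT-Q test, the major-complication rate or the sample size changes. Nothing here bears on which array should be used.

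**What to change.** - **Table 15:** show the impedance means and the deactivated or out-of-range counts separately for CLA and EVO, with the number of patients measured in each at each visit.
- **SAP 6.3.5:** state the model in full, with patient as a random effect and visit, channel, array and array-by-channel as fixed effects. List the contrasts of interest, which the protocol left to the SAP.
- **Protocol 3.5.3.1:** reconcile with 3.5.2 and Appendix 1 by stating that two array configurations are used.
- **Footnote to Table 15:** array choice is the surgeon's and is related to insertion difficulty, so the array contrast is descriptive.

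The implant type is already collected under SAP 5.5, so no new data are needed. The model gains 1 + 19 = 20 fixed-effect parameters. The main drawback is thin data: at an assumed 90% EVO share of 55 patients, only 5 would have the CLA, and their means would be imprecise. Columns by array in Tables 8 and 9.1 would be an optional display and are not part of this point.
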